## 12.4. Efficacy Analyses

All efficacy analyses will be performed on both the FAS and PP analysis set. Efficacy data will also be presented in data listing.

### 12.4.1. Multiplicity

No adjustments or analysis to detect multiplicity will be performed.

### 12.4.2. Imputation Methods

For the continuous efficacy analysis on the FAS population, missing data will be imputed using last observation carried forward (LOCF). Missing data will not be imputed for continuous efficacy analyses that are based on the PP population. For responder-type categorical endpoints (such as EASI-50, EASI-75, and EASI-90), missing data will be treated as a non-response.

### 12.4.3. Primary Estimand

Given the primary objective described in [Section 7](#), we seek an estimand that will measure the effect of ATI-1777 administration on the signs and symptoms of AD as measured by the percent change from baseline in EASI scores in

adult patients with moderate to severe AD as compared to placebo in the absence of other interventions or interruptions. This estimand will not be directly measurable if, in the judgment of the investigator, interventions are required for the sake of the patient safety and/or comfort. This estimand will also not be directly measurable if missing data result from a patient withdrawing consent or losing interest in study participation (loss to follow-up). This section outlines the measures and methods that will be used to adjust the primary endpoint to account for these types of intercurrent events to obtain as close an estimand to the desired objective as possible.

#### 12.4.3.1. The Population

The patients of primary interest in this study are adult patients with moderate or severe AD. This population of patients is largely reflected by the inclusion/exclusion criteria in the protocol. Generally, the targeted population for this estimand is agnostic to the degree of compliance to treatment administration and adherence to protocol specified procedures; in the spirit of the Intention-To-Treat principle. However, the targeted population is required to have been treated with at least one dose of study medication (see FAS analysis population description in [Section 9.2.1](#)). There is no stratum of patients based on the potential for an intercurrent event that is needed to define the targeted population for this study. It is anticipated that the group of severe AD patients in this study will be more difficult to treat. The randomization strategy for this study incorporates stratification by AD severity to help balance in the treatment groups within the AD severity. This stratification group will also be accounted for in the population-level summary methods used to compute the estimand.

#### 12.4.3.2. Primary Endpoint

The primary endpoint is the percent change from baseline in EASI score at Week 4 on FAS. Missing data will be imputed using LOCF.

The EASI ([Hanifin et al 2001](#); [Rullo et al 2008](#)) assesses the extent and severity of AD. This study will employ a modified EASI that excludes evaluation of the scalp, face, palms of hands, soles of feet, groin, and genitalia. The modified EASI will evaluate AD in each of 3 body regions (trunk [excluding groin and genitalia], upper extremities [excluding palms of hands], and lower extremities [excluding soles of feet]). The EASI scoring system uses a defined process to grade the severity of the signs of AD and the extent affected. If possible, the same individual should conduct the extent and severity evaluations at each visit.

Each respective body region will be given a score between 0 and 6 based on the percentage involvement in that region according to [Table 4](#). Precise measurements are not required.

**Table 4 Extent of Atopic Dermatitis in Each Body Region**

| % Involvement | 0% | 1% to 9% | 10-29% | 30-49% | 50-69% | 70-89% | 90-100% |
|---------------|----|----------|--------|--------|--------|--------|---------|
| Region Score  | 0  | 1        | 2      | 3      | 4      | 5      | 6       |

For each respective body region, the severity of each of 4 signs (erythema, edema/papulation, excoriation, lichenification) will be graded by the investigator or qualified designee on a 0- to 3-point scale ([0] none, [1] mild, [2] moderate, [3] severe) in AD-affected areas. Half scores are allowed. The average severity across AD-affected areas in each body region will be used as the score for that region.

The final EASI score will then be calculated by an electronic data capture system as described in [Table 5](#).

**Table 5 EASI Score Calculation**

| Body Region   | Erythema | Edema/ papulation | Excoriation | Lichenification | Area Score | Multiplier | Score |
|---|----------|-------------------|-------------|-----------------|------------|------------|-------|
| Trunk   | ( X +    | X +               | Z +         | AA)?            | ×          | × 0.3      |       |
| Upper extremity                                     | ( +      | +                 | +           | )               | ×          | × 0.2      |       |
| Lower extremity                                     | ( +      | +                 | +           | )               | ×          | × 0.4      |       |
| Final EASI score is the sum of the 3 region scores: |          |                   |             |                 |            |            | —     |

EASI = Eczema Area and Severity Index

#### 12.4.3.3. Imputation for Intercurrent Events

An intercurrent event is one that occurs after the first dose of study medication and either precludes the observation of the primary variable/endpoint or affects its interpretation. The following is a list of intercurrent events that could occur during this study:

- Death
- Withdrawal from study
- Withdrawal of study medication due to an AE
- Rescue with a non-protocol specified treatment for AD

Missing data and data following these intercurrent events will be imputed using the LOCF methodology.

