For the primary efficacy analysis and all continuous analyses based on the FAS population, missing data will be imputed using last observation carried forward (LOCF). Missing data will not be imputed for continuous efficacy analyses that are based on the PP population. For responder-type categorical endpoints (such as EASI-50, EASI-75, and EASI-90), missing data will be treated as a non-response. Specific details regarding the imputation of missing data and intercurrent events will be described further in the SAP.

Patients who prematurely discontinue the study will be evaluated based on the data collected at each visit attended. Data collected during the ET Visit will be used as an end-of-study assessment for these patients. If the ET Visit was performed >1 day after the last dose was administered, then the previous visit will be used as the end-of-study assessment.

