#### 12.4.3.4. Primary Analysis

The primary efficacy analysis will be the treatment comparison between ATI-1777 and vehicle for the percent change from baseline in EASI scores at Week 4 based on the FAS. Change from baseline is calculated as described in [section 10.1.3](#). This treatment comparison will be made within the context of a Mixed Model Repeated Measures (MMRM) analysis where the EASI scores over time are treated as repeated measures within a given patient. Treatment group, time (study visit), treatment by time interaction, and baseline severity of AD will enter the model as categorical factors, baseline EASI score will be included as a continuous covariate, and patient ID will enter the model as a random effect. Treatment group model-based means and model-based differences in treatment groups will be provided along with corresponding 90% confidence intervals and p-values. If the MMRM model will not converge or if there is strong collinearity between the baseline EASI score and the baseline severity of AD, one or both of the covariates may be excluded from the primary analysis.

For the primary efficacy analysis on the FAS population, missing data will be imputed using LOCF. Missing data will not be imputed for the analyses that are based on the PP population.

The null hypothesis is that the LSM contrast between ATI-1777 and vehicle at Week 4 equals zero. Significance tests will be based on least-squares means using a one-sided test at  $\alpha = 0.05$  (one-sided p-value compared to 0.05). A symmetric two-sided 90% confidence interval will accompany the corresponding p-value. The MMRM will be fit with covariance matrices of UN (unstructured), CS (compound symmetry), TOEPH (Heterogeneous Toeplitz) and ARH(1) (Heterogeneous auto-regressive 1). The analysis with the lowest Akaike's information criterion (AIC) will be reported in the table. Other covariance matrix structures may be used if none of these converge. The Kenward-Roger approximation will be used to estimate the denominator degrees of freedom.

The estimates at the timepoint Week 4 will be considered as primary. Least squares mean, Standard Errors, for each treatment group, least squares mean difference (ATI-1777 minus vehicle), and 90% confidence intervals for the

difference between the treatment groups and the corresponding one-sided p-value will be reported. The following SAS code will be used.

```
proc mixed data= datain method=ml;
  class treatment visit baseline ADseverity;

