#### 12.4.3.5. Sensitivity Analyses

The population-level summary for the primary estimand based on the FAS population will be repeated using the Per-Protocol population to assess the sensitivity of the analysis to compliance to treatment administration and adherence to protocol specified procedures. Other secondary efficacy analyses and summaries are intended to support the primary estimand and do not qualify as sensitivity analyses.

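### The primary MMRM is fitted to LOCF-completed FAS data, which in general misses the SAP's own Week 4 estimand, and no planned FAS analysis of the primary endpoint varies that assumption

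*SAP*

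**What the plan says.** **Estimand.** SAP 12.4.3 asks for the effect on percent change in EASI "in the absence of other interventions or interruptions". It accepts that this cannot be observed directly once a patient needs other treatment or leaves, and offers its methods as a way "to obtain as close an estimand to the desired objective as possible". SAP 12.4.3.1 adds that the target population is "agnostic to the degree of compliance to treatment administration and adherence to protocol specified procedures".

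**Missing data.** SAP 12.4.3.2 defines the primary endpoint as the EASI "score at Week 4 on FAS. Missing data will be imputed using LOCF". SAP 12.4.3.3 lists four intercurrent events (death, leaving the study, stopping drug because of an AE, rescue) and then says "Missing data and data following these intercurrent events will be imputed using the LOCF methodology". SAP 12.4.3.4 repeats: "For the primary efficacy analysis on the FAS population, missing data will be imputed using LOCF". Protocol 9.4.9 applies the same rule "For the primary efficacy analysis and all continuous analyses based on the FAS population". Neither document states or justifies an assumption about how EASI moves after the last score.

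**Sensitivity.** Under SAP 12.4.3.5 the primary summary "will be repeated using the Per-Protocol population to assess the sensitivity of the analysis to compliance to treatment administration" and to protocol adherence. The same section says that the other secondary analyses do not count as sensitivity analyses. PP (SAP 9.2.2) requires a Week 4 EASI and no major deviation, and PP data are not imputed (SAP 12.4.2).

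**Responder endpoints.** EASI-50, -75 and -90 score missing data as non-response (SAP 12.4.2).

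**The concern.** LOCF enters a Day 8, Day 15 or qualifying early-termination (ET) score as if it were the Week 4 score. If patients would have gone on improving without the event, the value is too low, and by more in the arm that is improving faster or losing more patients. The MMRM already handles incomplete repeated measures, so filling the gaps first gives up its main advantage.

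At stake are the primary contrast, its 90% interval and the one-sided test. The direction of error is not fixed, and the one planned check discards the patients for whom LOCF was used.

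**Working it through.** **1. The plan's own figure.** With 17 per arm, difference 65 − 20 = 45, spread 38.3 and one-sided 0.05 (SAP 8.3 and 12), the noncentrality is 45 / (38.3 × √(2/17)) = 45 / 13.14 = 3.43 on 32 df. Power is 95.6%, as stated. This needs 38.3 to be an SD, although the text calls it a variance.

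**2. Formula.** Let d be the share of an arm carried forward from a given visit and g the mean improvement still to come after it. Summed over exit visits:

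expected LOCF contrast = true contrast − (d_A·g_A − d_V·g_V).

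The error is zero if g = 0 in both arms, or if the two products happen to be equal.

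**3. Equal random loss, no ET scores.** The enrolment margins are (42 − 34)/42 = 19% (SAP 8.3) and (50 − 34)/50 = 32% (Protocol 9.3). With equal hazards after Day 8 and Day 15, 19% splits into 10.0% and 9.0%, and 32% into 17.5% and 14.5%. Only the Week 4 means come from the documents; the time courses are assumed.

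| Course | Day 8/15/28 means, active vs vehicle | Contrast to come after Day 8, Day 15 | LOCF at 19% | LOCF at 32% |
|---|---|---|---|---|
| Fast | 45/58/65 vs 14/18/20 | 14, 5 | 45 − (0.100×14 + 0.090×5) = 43.2 | 45 − (0.175×14 + 0.145×5) = 41.8 |
| Base | 30/48/65 vs 10/15/20 | 25, 12 | 45 − (0.100×25 + 0.090×12) = 41.4 | 45 − (0.175×25 + 0.145×12) = 38.9 |
| Slow | 20/40/65 vs 6/12/20 | 31, 17 | 45 − (0.100×31 + 0.090×17) = 40.4 | 45 − (0.175×31 + 0.145×17) = 37.1 |

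The shortfall is 1.8 to 7.9 points. If every dropout gives an on-drug ET score, the base course gives 42.6 and 40.9. Straight-line improvement from Day 1, with losses split evenly between the two visits, leaves 33.3 and 21.7 to come, so at 32% LOCF gives 45 − 0.16 × (33.3 + 21.7) = 36.2, or 8.8 low.

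**4. Cancellation.** Take straight-line improvement, exits after Day 8 (20/27 of the gain still to come) and losses of 2/21 active and 6/21 vehicle. The error is 2/21 × 65 × 20/27 − 6/21 × 20 × 20/27 = 4.59 − 4.23, about 0.35 points.

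**5. No true effect, more vehicle loss.** Both arms follow 10/15/20, with random loss of 24% active (12.8% + 11.2%) and 40% vehicle (22.5% + 17.5%). The carry-forward errors are 0.128×10 + 0.112×5 = 1.84 and 0.225×10 + 0.175×5 = 3.13, a shift of 1.29 towards ATI-1777. With 25 per arm the SE is 38.3 × √(2/25) = 10.83, and P(Z > 1.645 − 1.29/10.83) = 6.4%.

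**6. Simulation.** 20,000 trials per case, base course, SD 38.3, assumed correlations 0.7/0.5/0.7 (Days 8–15, 8–28, 15–28), no covariates, unstructured covariance. Response-driven dropout depends on the last observed score, so it is missing at random (MAR). No ET scores in this table; splits are active vs vehicle.

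| Case | True | LOCF | PP | LOCF error | FAS − PP gap |
|---|---|---|---|---|---|
| Equal random, 32% | 45 | 38.9 | 44.9 | −6.1 | −6.0 |
| Response-driven, 24% vs 40% | 45 | 42.9 | 41.4 | −2.1 | +1.5 |
| Response-driven, 40% vs 24% | 45 | 35.0 | 48.3 | −10.0 | −13.3 |
| Null at 20%, response-driven, 24% vs 40% | 0 | +2.4 | −3.6 | +2.4 | +6.0 |

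The gap matches the LOCF error only in the first row. In the second it has the wrong sign.

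Null error with more vehicle loss (14% vs 24% and 24% vs 40%, with and without ET scores) was 5.5% to 7.5%; a repeat of the 24% vs 40% cases gave 6.4% to 8.0%. With more active loss it was 3.3% to 4.5%. Coverage of the 90% interval under equal random loss was 89% at 19% and 88% to 85% at 32%.

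**7. The alternative.** In these MAR cases the MMRM on observed data had null error of 4.4% to 4.8% and coverage of 90% to 91%. When dropout depends on the unobserved next score (MNAR), it is biased too: 42.2 (LOCF 41.1) at 24% vs 40%, and 47.7 (LOCF 36.7) at 40% vs 24%. Null error was then 2.7% and 7.4%, against 5.7% and 4.5% for LOCF.

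**The case against.** The strongest reply is that the SAP presents its method as an approximation, the efficacy objective is preliminary (Protocol 2.1), and LOCF is not clearly less accurate overall. In no-ET runs (4,000 trials each), root mean squared error for LOCF against observed-data MMRM was 12.4 vs 12.5 (equal random, 19%), 12.5 vs 12.2 (equal random, 32%) and 12.3 vs 12.5 (response-driven, 24% vs 40%). LOCF power under equal random loss at the base course was about 96%. All of this stands. LOCF was clearly worse only with more active loss (16.1 vs 12.6 at 40% vs 24%), and modestly worse with equal response-driven loss (13.5 vs 12.7). Similar squared error does not remove the bias or restore coverage, however, and the plan has no analysis that would reveal either.

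A reader might also infer several stronger things that the documents do not support:

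- *LOCF is wrong whenever EASI is not flat.* True of an arm mean, not of the contrast (step 4).
- *No FAS analysis uses another missing-data rule.* The responder analyses do. But they concern different endpoints, and SAP 12.4.3.5 denies them sensitivity status.
- *LOCF makes a false positive likely.* Only with more vehicle loss. Error rates up to about 22% need losses of 4/25 vs 12/25, a 40-point response in both arms and straight-line improvement, none of which is in the documents.
- *The observed-data MMRM is always better.* Step 7 shows that it is not. In a second simulation (straight-line course), with dropout driven by the unseen Week 4 value, LOCF gave 43.8 and 43.5 and the MMRM 41.5 and 37.8, against a true 45.
- *Off-drug scores certainly stay in after an unlisted stop.* Protocol 4.1.2 sends such patients to an ET visit and then follow-up, while Protocol 5.4.1 and SAP 10 keep them on scheduled visits. That conflict is a separate matter, not evidence against LOCF.

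**Conclusion.** The mismatch is real and worth correcting, but moderate for a Phase 2a study. The stated target is hypothetical, the estimator assumes no further mean change after the last score (or a lucky cancellation), and no FAS analysis of the primary endpoint tests that.

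The sizes are illustrative. Under equal random loss LOCF is conservative at the design effect, by about 2 to 8 points over the three courses and ET assumptions, with little loss of power at the base course. The 10-point shortfall, where power falls to about 87%, arises only with 40% vs 24% response-driven loss and no ET scores, although the protocol asks for an ET visit. Under no effect at the plan's 20% response, error rises to about 5.5% to 8% only with more vehicle loss. Time course, correlations, dropout mechanism and arm split are all assumed, and the simulation omits the planned covariates and the AIC choice of covariance.

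**What to change.** 1. **Primary:** fit the same MMRM to observed FAS data without imputation. Set scores after a listed intercurrent event to missing. Use an ET score only in the Table 2 window of its actual day, and only if it precedes the event, with that term defined once.
2. **Sensitivity:** keep LOCF as a sensitivity analysis and PP as supportive. Add one FAS analysis of the primary endpoint that departs from MAR (delta-adjusted or reference-based multiple imputation), because the observed-data MMRM is itself biased under MNAR.
3. **Separately, reconcile the estimand text:** SAP 12.4.3 excludes interruptions, 12.4.3.1 uses intention-to-treat wording, and 12.4.3.3 lists drug withdrawal only for an AE. State how scores after a temporary interruption or a non-AE stop are handled. Protocol 4.1.2 must also be reconciled with Protocol 5.4.1 and SAP 10 on which visits follow a stop.
4. Change Protocol 9.4.9 and SAP 10, 12.4.2 and 12.4.3 to 12.4.3.5 together, before database lock.

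**Cost:** wording and one extra analysis, with no change to conduct or sample size. The interval widens somewhat under equal random loss: mean SE 12.9 vs 12.0 at 19%, and 12.6 vs 11.1 at 32%. Simulated MMRM power under the design assumptions and MAR dropout stays at about 96%.

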#### 12.4.3.4. Primary Analysis

The primary efficacy analysis will be the treatment comparison between ATI-1777 and vehicle for the percent change from baseline in EASI scores at Week 4 based on the FAS. Change from baseline is calculated as described in [section 10.1.3](#). This treatment comparison will be made within the context of a Mixed Model Repeated Measures (MMRM) analysis where the EASI scores over time are treated as repeated measures within a given patient. Treatment group, time (study visit), treatment by time interaction, and baseline severity of AD will enter the model as categorical factors, baseline EASI score will be included as a continuous covariate, and patient ID will enter the model as a random effect. Treatment group model-based means and model-based differences in treatment groups will be provided along with corresponding 90% confidence intervals and p-values. If the MMRM model will not converge or if there is strong collinearity between the baseline EASI score and the baseline severity of AD, one or both of the covariates may be excluded from the primary analysis.

For the primary efficacy analysis on the FAS population, missing data will be imputed using LOCF. Missing data will not be imputed for the analyses that are based on the PP population.

The null hypothesis is that the LSM contrast between ATI-1777 and vehicle at Week 4 equals zero. Significance tests will be based on least-squares means using a one-sided test at  $\alpha = 0.05$  (one-sided p-value compared to 0.05). A symmetric two-sided 90% confidence interval will accompany the corresponding p-value. The MMRM will be fit with covariance matrices of UN (unstructured), CS (compound symmetry), TOEPH (Heterogeneous Toeplitz) and ARH(1) (Heterogeneous auto-regressive 1). The analysis with the lowest Akaike's information criterion (AIC) will be reported in the table. Other covariance matrix structures may be used if none of these converge. The Kenward-Roger approximation will be used to estimate the denominator degrees of freedom.

The estimates at the timepoint Week 4 will be considered as primary. Least squares mean, Standard Errors, for each treatment group, least squares mean difference (ATI-1777 minus vehicle), and 90% confidence intervals for the

difference between the treatment groups and the corresponding one-sided p-value will be reported. The following SAS code will be used.

```
proc mixed data= datain method=ml;
  class treatment visit baseline ADseverity;
  model pchg_EASI = baseline_EASI baseline_ADseverity visit treatment treatment*visit
    / cl solution ddfm=kr alpha=0.10;
  repeated /type=un subject=usubjid;
  slice treatment * visit /sliceby=visit means diff nob cl;
  ods output slices = lsm sliceDiffs = diff;
run;
```

Summary statistics (n, mean, SD, minimum, Q1, median, Q3, and maximum) of the baseline value, the value at Week 4 and the corresponding change from baseline for EASI score will be presented by treatment group and overall using the FAS..

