### 8.3. Sample Size Considerations

A total of approximately 42 patients will be enrolled and randomized in order to achieve 34 patients who complete the study. Data from 34 patients provides 95.6% power to detect a statistically significant difference between the treatment groups in the primary endpoint (percent change from baseline in EASI scores). This power calculation is based upon a 1-sided treatment contrast within 1-way ANOVA model and assumes group means of 65% and 20% for ATI-1777 and vehicle, respectively. The group means were based upon slightly more conservative estimates than were observed in a Phase 2 study of topical ruxolitinib in AD. (Kim et al 2020b) The variance for the percent change from baseline in EASI was assumed to be 38.3%. This variance assumption was based upon data observed in a pilot AD study for the topical compound ATI-502 (ATI-502-AD-201).

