## 12. Statistical Methods

All analyses will use SAS version 9.4 or higher.

Categorical variables will be summarized using counts and percentages based on the specified population total. Percentages will be rounded to one decimal place, except 100% will be displayed without any decimal places and percentages will not be displayed for zero counts.

Continuous data will be summarized using non-missing observations (n, mean, standard deviation (SD), median, Quartile 1, Quartile 3, minimum, and maximum). The median, minimum, and maximum values will be displayed to the same level of the precision as the raw value. Mean, median, Q1 and Q3 will be rounded to 1 decimal place greater than the precision of the original value. The SD will be rounded to 2 decimal places greater than the precision of the original value. Confidence intervals, least square mean (LSM) and standard error (SE) will be provided as appropriate. Confidence intervals, LSM will present the same precision as the mean value whereas SEs will present the same precision as SD.

P-values will be rounded to 3 decimal places. P-values less than 0.001 will be presented as “<0.001” and p-values greater than 0.999 will be presented as “>0.999.”

Statistical hypothesis testing will be one-sided and carried out at the 5% level of significance. Testing will be performed on the primary endpoint and secondary endpoints as appropriate. No adjustments for multiplicity will be made.

If there is strong collinearity between the baseline EASI score/BSA score/IGA score and the baseline severity of AD (moderate versus severe), the continuous baseline score will be included the efficacy analysis.

All the listings will be displayed by treatment arm, patient identifier and date of assessment. Age, gender, and race will be presented on each listing.

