#### 12.4.4. Secondary Analyses

Treatment comparisons between ATI-1777 and vehicle for each of the continuous efficacy endpoints that are conducted over time (change in IGA, BSA, and PP-NRS) will be analyzed using a similar model as described for the primary endpoint. Treatment comparisons will be made for each post-baseline scheduled visit utilizing the analysis window scheme described in [Section 10.1.1](#). Change from baseline is calculated as described in [section 10.1.3](#).

Treatment group comparisons for categorical efficacy endpoints (IGA response, EASI-50, EASI-75, and EASI-90) that are conducted over time will employ a logistic regression model fit at each scheduled visit separately, where appropriate. The logistic regression model will include treatment group and baseline severity of AD as a factor, and the baseline value as a covariate. Model-based point estimates for the treatment proportions will be provided as well as model-based differences and corresponding symmetric 90% confidence intervals and one-sided p-values. If the Logistic model will not converge or if there is strong collinearity between the baseline EASI score and the baseline severity of AD, one or both of the covariates may be excluded from the secondary analysis.

The secondary efficacy endpoints are

- Percent change from baseline in EASI score at each study visit
- Proportion of patients achieving an IGA score of 0 to 1 combined with an improvement of 2 or more points from baseline within 4 weeks of the start of treatment
- Proportions of patients who achieve EASI-50, EASI-75, and EASI-90 within 4 weeks of the start of treatment
- Change from baseline in IGA score at each study visit
- Change from baseline in BSA at each study visit
- Change from baseline in PP-NRS score over time

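### The SAP gives incompatible rules for dropping baseline EASI and AD severity from the primary model when they are collinear, and collinearity is no reason to drop either

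*SAP*

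**What the plan says.** SAP 12.4.3.4 specifies a mixed model for percent change in EASI with treatment, visit, their interaction, baseline AD severity (categorical) and baseline EASI (continuous). The SAS code there contains both covariates. The section then adds that, if the model does not converge or the two covariates are strongly collinear, "one or both of the covariates may be excluded from the primary analysis".

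Three other places bear on the same choice:

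- SAP 12 deals with collinearity between a baseline score (EASI, BSA or IGA) and severity. In that case "the continuous baseline score will be included the efficacy analysis".
- SAP 12.4.3.1 notes that randomisation is stratified by severity and commits to using it: "This stratification group will also be accounted for in the population-level summary methods used to compute the estimand".
- SAP 12.4.4 repeats the exclusion option for the logistic models: "one or both of the covariates may be excluded from the secondary analysis".

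Protocol 9.4.5 leaves the covariates open with an and/or between baseline EASI and severity. Neither document defines strong collinearity, gives an order of removal, or says who decides and when.

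**The concern.** For the single trigger of collinearity, Section 12 fixes baseline EASI in the model, while 12.4.3.4 allows it to be removed. If severity is removed under either section, the commitment in 12.4.3.1 is broken and the analysis no longer reflects the stratified randomisation. Four covariate sets (both, EASI only, severity only, neither) fit the wording of 12.4.3.4, so the model behind the one primary p-value is not fully fixed once a trigger is declared.

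The trigger also lacks a statistical basis. Collinear covariates make each other's coefficients imprecise, but those coefficients are not of interest here. Dropping both because they overlap is the least defensible option, since it throws away the information that they share.

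**Working it through.** **Inputs from the documents.** "Statistical hypothesis testing will be one-sided and carried out at the 5% level of significance" (SAP 12). "Data from 34 patients provides 95.6% power to detect a statistically significant difference", and "This power calculation is based upon a 1-sided treatment contrast within 1-way ANOVA model" that "assumes group means of 65% and 20% for ATI-1777 and vehicle, respectively" (SAP 8.3). Allocation is 1:1. The figure 38.3 is labelled a variance, but it reproduces the stated power only as a standard deviation.

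**Planned power.** With 17 per arm, SE = 38.3 × √(2/17) = 13.14 and the noncentrality is 45/13.14 = 3.42. The noncentral t with 32 degrees of freedom gives 95.61%, matching the plan. No covariate enters this figure.

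**Effect of adjustment.** If the covariates together explain a share R² of outcome variance, SE = 13.14 × √(1 − R²). The documents give no R², so 0 to 0.3 is an assumed range.

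| R² | SE, both kept | CI widening if both dropped | Power, both kept |
|---|---|---|---|
| 0 | 13.14 | 0% | 95.6% |
| 0.1 | 12.46 | 5% | 97.0% |
| 0.2 | 11.75 | 12% | 98.2% |
| 0.3 | 10.99 | 20% | 99.1% |

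**Why collinearity is not the issue.** The variance of the treatment coefficient is σ² / [Σ(T − T̄)² × (1 − R²_T)], where R²_T measures how well the covariates predict treatment assignment. Randomisation keeps R²_T small however strongly the covariates correlate with each other.

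**Simulation.** Single-visit ANCOVA at Week 4, stratified permuted blocks of 4, 30% severe, the two covariates equally weighted, 6,000 null trials per scenario (Monte Carlo SE about 0.3 percentage points). All these settings, and the EASI–severity correlations, are assumptions. Mean model-based SE of the treatment difference at N = 34:

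| Correlation | R² | Both | EASI only | Severity only | Neither | One-sided error, neither | Smallest of four p-values |
|---|---|---|---|---|---|---|---|
| 0.5 | 0.1 | 12.54 | 12.65 | 12.51 | 13.02 | 4.1% | 6.2% |
| 0.5 | 0.3 | 11.11 | 11.66 | 11.48 | 13.10 | 3.2% | 6.8% |
| 0.8 | 0.1 | 12.59 | 12.52 | 12.45 | 13.04 | 4.7% | 6.5% |
| 0.8 | 0.3 | 11.08 | 11.20 | 11.14 | 13.07 | 2.6% | 6.0% |

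- *Collinearity.* Moving the correlation from 0.5 to 0.8 raises the variance inflation factor from 1/(1 − 0.25) = 1.33 to 1/(1 − 0.64) = 2.78. At R² = 0.3 the treatment SE with both covariates goes from 11.11 to 11.08, so it is unaffected.
- *Dropping one.* At R² = 0.3 the worst case in the table is (11.66/11.11)² = 1.10, or 10% more variance. At correlation 0.8 it is (11.20/11.08)² = 1.02. Across further runs with correlations 0.6 to 0.9 the loss was 0 to about 12%.
- *Dropping both.* At R² = 0.1, (13.02/12.54)² = 1.08 and (13.04/12.59)² = 1.07. At R² = 0.3, (13.10/11.11)² = 1.39 and (13.07/11.08)² = 1.39. At N = 50 the increases are about 9% and 40–41%.
- *Nature of the loss.* Much of it lies in the reported SE. At correlation 0.8 and R² = 0.3 the empirical SE is 11.28 with neither and 11.18 with both, because stratification already balances severity. The unadjusted model reports 13.07, which is why its test is conservative.
- *Price of keeping both.* If neither covariate predicts anything, SE is 13.27 with both against 13.04 with neither, (13.27/13.04)² = 1.04, or about 4% more variance.

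**The case against.** The two rules can be partly reconciled: on collinearity follow Section 12 and keep EASI, and use the wider option in 12.4.3.4 only for non-convergence. But 12.4.3.4 names collinearity explicitly as a trigger for removing one or both, so this reading has to be supplied by the reader. Even then severity would go, against 12.4.3.1.

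A default model is stated. SAP 9.3 lists both covariates, SAP 6.1 records that severity was added, and the code fits both. That stands: the exclusions are a contingency.

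A reader might infer that the plan allows the analyst to try four models after unblinding and report the best p-value. The documents do not support that. Exclusion needs a trigger, and collinearity depends on baseline data alone, so it can be judged blinded. Two weaker points remain: nothing requires a blinded judgement, and convergence of the model with the true treatment term can be seen only after unblinding. The 6–7% error is therefore a worst case. Limited to the choice between both covariates and EASI only, a separate run gave 4.5–6.1%.

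A reader might also infer that exclusion costs planned power. It does not: the 95.6% rests on an unadjusted ANOVA, so only the gain from adjustment is lost.

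Finally, an exclusion clause has some use elsewhere. Entry requires IGA 3 or 4, labelled moderate or severe (Protocol 5.1), so baseline IGA and severity may coincide in the IGA model. Sparse outcomes such as EASI-90 may also cause separation in the logistic models. Both stand, and both call for specific rules.

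**Conclusion.** The concern holds as an inconsistency in stated rules. SAP 12.4.3.4 allows exclusions that SAP 12 and 12.4.3.1 rule out, on a trigger that does not materially affect the treatment contrast.

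The size depends on what is dropped. One covariate costs 0 to about 12% in variance. Both cost about 7–9% at R² = 0.1 and about 40% at R² = 0.3, with one-sided error of roughly 3–4% instead of 5%. Selecting the best of four models would give about 6–7%, as a worst case.

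These figures rest on assumed R², correlation and severity mix, and on a single-visit ANCOVA in place of the full mixed model with LOCF. The contradiction between the sections depends on none of them. This is worth correcting before unblinding, but it does not threaten the planned power.

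**What to change.** - **Primary EASI model.** Keep baseline EASI and AD severity regardless of collinearity. Delete the collinearity clauses in SAP 12, 12.4.3.4 and 12.4.4, and replace the and/or phrase in Protocol 9.4.5 and the Protocol Summary.
- **Non-convergence of the mixed model.** SAP 12.4.3.4 already fits four covariance structures and allows others if none converges. Write the simplifications down in a fixed order and use them first. If a covariate must still be removed, follow an order named before unblinding that keeps the stratification factor.
- **Logistic models.** A covariance-structure fallback cannot apply here. Pre-specify a separate one for separation or non-convergence, for example Firth penalised logistic regression with the same covariates.
- **IGA model.** If baseline IGA and severity are exactly aliased, fit one of them; the treatment contrast is the same either way.

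The cost is SAP wording and a short protocol phrase. Both covariates are already collected, and no extra data or patients are needed.
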